Study Objectives: Safety Objective 
• To evaluate the safety (immunogenicity and thrombogenicity) associated with long term use of Fanhdi Primary Efficacy Objective 
• To evaluate the overall clinical efficacy of Fanhdi in bleeding episodes
Overall Study Design and Description: This is a Phase 4, observational, multi-center, prospective, post-authorization cohort study examining the safety (immunogenicity and thrombogenicity) and overall clinical efficacy of long term use of Fanhdi in routine clinical practice in approximately 15 subjects with von Willebrand disease (VWD). In this clinical study, subjects will be treated with Fanhdi according to the investigator's standard of care to achieve hemostasis. Enrolled subjects will be treated with Fanhdi as their sole source of von Willebrand factor/coagulation factor FVIII (VWF/FVIII) concentrate for prophylaxis and treatment of all bleeding episodes and surgical or invasive procedures for an observational period of 12 months. Data will be collected from the information generated during routine examinations and treatments as performed by the investigator per standard of care during an observation period of 12 months, starting with the first Fanhdi infusion. There will be no intervention with the prescribing habits or practices of the investigator's standard of care; however the investigator is expected to treat the subject within the approved labeling for dose and frequency of Fanhdi. Data collection for all subjects will include inhibitor development (immunogenicity), thrombogenicity, adverse events (AEs), bleeding episodes (spontaneous or traumatic bleeding), surgery or invasive procedure, duration and severity, assessment and achievement of hemostasis, and Fanhdi consumption.
Number of Subjects Planned: Approximately 15 subjects are planned to be enrolled in this clinical study.

Diagnosis and Main Criteria for Inclusion:

Inclusion Criteria:

A subject who will be treated with Fanhdi must meet all the following inclusion criteria to be eligible for participation in this study:

1. Male or female subjects ≥ 18 years of age diagnosed with hereditary VWD of any type and severity who require replacement therapy with VWF/FVIII concentrates when desmopressin (DDAVP) treatment alone is ineffective or contra-indicated.
2. Subjects with a history of receiving prior treatment with VWF concentrates due to bleeding episodes and/or surgery or invasive procedures (on demand or prophylaxis).
3. Subjects who are expected to experience bleeding episodes and/or surgeries or invasive procedures (including elective surgeries) requiring replacement therapy in the future or with active bleeding at the time of inclusion.
4. Subjects who are willing and able to provide written informed consent or have an authorized representative able to provide written informed consent on behalf of the subject in accordance with local law and institutional policy.

Exclusion Criteria

Subjects with data meeting any of the following exclusion criteria are NOT eligible for participation in this study:

1. Subjects diagnosed with acquired VWD.
2. Subjects with a congenital or acquired platelet function disorder or other concomitant processes that may interfere with coagulation.
3. Subjects who are positive for anti-VWF or anti-FVIII antibodies (≥ 0.5 Bethesda units) or has been positive in the history of their disease.
4. Subjects with a known intolerance to any substance contained in Fanhdi.
5. Subjects with a history of anaphylactic reactions to blood or blood components.
6. Subjects who are participating in another clinical study involving an investigational treatment or have participated in one in the past 4 weeks.
7. Subjects who, in the opinion of the investigator, the subject may have compliance problems with the protocol.

Study Treatment, Dose, and Mode of Administration:

Fanhdi (Double-inactivated Human Anti-hemophilic Factor [VWF/FVIII]) will be administered intravenously; doses of 40 to 80 IU/kg VWF (VWF:RCo) and 20 to 40 IU/kg FVIII:C are recommended.

Duration of Treatment:

Subjects will be treated according to the investigator's standard of care and followed for a 12 month observation period.

Key Study Variables:Safety Variables:

- Adverse events including serious AEs and suspected adverse drug reactions (ADRs)
- Clinical laboratory values including inhibitor (immunogenicity) and functional activity testing
- Thrombogenicity assessment
- Vital signs
- Physical examination

Efficacy Variables:

- Bleeding duration
- Bleeding severity
- Investigator's qualitative assessment of hemostasis utilizing a 4-point rating scale (evaluated as "excellent," "good," "poor," or "no response" in response to therapy with Fanhdi received by the subject in a hospital or another location under the investigator's direct supervision).
- Amount of Fanhdi (IU/kg) used per subject and per year
- Amount of Fanhdi (IU/kg) used per infusion
- Use of other hemoderivatives per bleeding episode
- Overall clinical efficacy

Study Assessments and Procedures:

In this clinical study, subjects will receive the most suitable dose of Fanhdi, according to the investigator's discretion, to achieve satisfactory hemostasis. There will be no intervention with the prescribing habits or practices of the investigator's standard medical care; however the investigator is expected to treat the subject within the approved labeling for dose and frequency of Fanhdi.

Subjects will be followed for 12 months after the first infusion of Fanhdi, in which information gathered from any episode (spontaneous or traumatic bleeding), surgery or invasive procedure, and the response to treatment and consumption of Fanhdi will be collected.

An assessment of the overall clinical efficacy of Fanhdi throughout the study will be performed and collected by the investigator utilizing a 4-point rating scale (evaluated as "excellent," "good," "poor," or "no response" in response to therapy with Fanhdi received by the subject in a hospital or another location under the investigator's direct supervision).

Statistical Methods:

Study Population

The Safety population will include all subjects enrolled in the clinical study and will be used for all safety and efficacy analyses.

Safety Analysis

The safety analyses will be addressed by listing and tabulation of AEs (includes suspected ADRs), clinical laboratory tests including inhibitor (immunogenicity) and functional activity testing, thrombogenicity, vital signs, and physical examinations. Data will be described using descriptive analyses.

Efficacy Analyses

For bleeding episodes, the bleeding duration, severity, achievement of adequate hemostasis, and overall clinical efficacy will be summarized. Also, the number of Fanhdi infusions and the total amount of Fanhdi dosed will be summarized. The proportion of bleeding episodes in which good or excellent clinical efficacy were achieved will also be summarized.

For surgeries or invasive procedures, the surgery type, severity of bleeding episodes, achievement of adequate hemostasis, and overall clinical efficacy will be summarized. Also, the number of Fanhdi infusions and the total amount of Fanhdi dosed will be summarized. The proportion of surgeries or invasive procedures in which good or excellent clinical efficacy were achieved will also be summarized.

For long-term observation, the long-term overall clinical efficacy will be summarized. Also, the number of bleeding episodes and surgeries or invasive procedures will be summarized. The number of infusions, exposure days, and dose per month will be summarized, in addition to the mean quantity of Fanhdi per bleeding episode and/or surgery or invasive procedure.

Determination of Sample Size

Approximately 15 subjects are planned to be enrolled in this clinical study. The sample size is based on clinical considerations and was not formally calculated.

TABLE OF CONTENTS

INVESTIGATOR SIGNATURE PAGE	3
PROTOCOL SYNOPSIS	4
TABLE OF CONTENTS.....	8
GLOSSARY AND ABBREVIATIONS.....	11
INTRODUCTION	12
1.1 Background.....	12
1.1.1 Von Willebrand Disease	12
1.1.2 Von Willebrand Disease Treatment.....	13
1.2 Rationale	14
2 OBJECTIVES.....	14
2.1 Safety Objective.....	14
2.2 Efficacy Objective	15
3 STUDY DESIGN.....	15
3.1 Study Design and Plan	15
3.1.1 Approved Fanhdi Dosing in the Treatment of Von Willebrand Disease.....	15
3.2 Selection of Study Population.....	15
3.2.1 Inclusion Criteria	15
3.2.2 Exclusion Criteria	16
3.2.3 Subject Withdrawal Criteria	16
3.3 Study Variables.....	17
3.3.1 Safety Variables	17
3.3.2 Efficacy Variables.....	17
3.4 Methods and Timing for Recording Study Parameters.....	18
3.5 Study Data Collection.....	18
3.5.1 Safety Assessments.....	18
3.5.1.1 Adverse Events	18
3.5.1.2 Clinical Laboratory Values Including Inhibitor (Immunogenicity) Testing.....	19
3.5.1.3 Thrombogenicity Assessment.....	19
3.5.1.4 Vital Signs.....	19
3.5.1.5 Physical Examination.....	20
3.5.2 Efficacy Assessments.....	20
3.5.2.1 Bleeding Episodes.....	20
3.5.2.2 Surgical or Invasive Procedures.....	21
3.5.2.3 Long-term Overall Clinical Efficacy	23
3.5.3 Subject Numbering	23
3.5.4 Data Collection Procedures.....	23
3.5.4.1 Data Sources	23
3.5.4.2 Data Collection Procedures.....	23

3.5.5	Data Quality	24
4	PROCEDURES FOR ELICITING REPORTS OF AND FOR RECORDING AND REPORTING ADVERSE EVENT AND INTERCURRENT ILLNESSES.....	24
4.1	Warnings/Precautions	24

1 INTRODUCTION

1.1 Background

1.1.1 Von Willebrand Disease

Von Willebrand disease (VWD) is the most common hereditary bleeding disorder. It affects both genders and is characterized by qualitative or quantitative abnormalities of von Willebrand factor (VWF), a high molecular weight glycoprotein involved in primary and secondary hemostasis. Von Willebrand factor is synthesized in endothelial cells and megakaryocytes, is stored in platelets, and circulates in plasma as multimers. It functions as a stabilizer and carrier of coagulation factor VIII (FVIII), with which it forms a noncovalently linked complex (1).

The physiological functions and biochemical properties of the FVIII and VWF plasma proteins, which form a macromolecular complex, are described below:

- Factor VIII coagulant (FVIII:C) participates in the activation of the plasma coagulation mechanism. Its activity is considerably reduced in patients with hemophilia A, and patients with hemophilia A require replacement therapy to prevent or resolve bleeding problems.
- Von Willebrand factor supports platelet adhesion to the vascular endothelium and plays an important role in platelet aggregation. Functional alterations of this factor lead to a decrease in FVIII:C activity and an increase in mucocutaneous bleeding (2).

The clinical expression of VWD is variable, manifesting as a bleeding tendency which can be mild, moderate, or severe. The bleeding is characteristically mucocutaneous, although patients with severe VWD tend to suffer from hemarthrosis, as do hemophilia patients, although it tends to be less intense. Epistaxis, menorrhagia, and bleeding following dental extractions are the most frequent symptoms (3,4). Von Willebrand disease is very heterogeneous and is classified depending on the genetic mutation and the degree of the VWF defect. There are 3 main VWD types (1, 2, and 3). Type 1 VWD is found in patients with a partial quantitative deficiency of VWF. Type 2 VWD is due to the qualitative deficiency of VWF and is further divided into 4 variants based on the phenotype (2A, 2B, 2M, and 2N). Type 3 VWF is due to a total deficiency of VWF. The degree of abnormality can be measured by analyzing bleeding time, plasma levels of VWF antigen (VWF:Ag), FVIII:C, ristocetin cofactor (VWF:RCof) activity, and the binding capacity of VWF to collagen (VWF:CBA). In addition, the multimeric distribution of VWF helps to characterize the type and subtype (5,6).

The most common type of VWD is Type 1, accounting for approximately 75% of all VWD cases (7). These patients are characterized by increased bleeding time and low levels of VWF:Ag, with proportional decreases in FVIII:C and VWF:RCof levels. The multimeric distribution of VWF is normal in the majority of cases (8,9).

In Type 2 VWD, the structure of the VWF molecule is abnormal, as high molecular weight multimeric forms are not detected. The majority of subtypes also show considerable reductions in VWF:RCof levels. Subtype 2A is characterized by decreased platelet function, attributable to the absence of high molecular weight VWF multimers. Subtype 2B exhibits an increased affinity of VWF for platelet glycoprotein Ib. Subtype 2M is characterized by a decrease in platelet function not attributable to the absence of high molecular weight VWF multimers. Subtype 2N results in variable bleeding dysfunction and is characterized by a VWF with decreased affinity for FVIII (variable VWF:Ag levels and VWF:RCof activity, with disproportionately low levels of FVIII:C) (10).

Type 3 VWD is the most severe form and it is characterized by undetectable or very low levels of VWF:Ag and FVIII:C and also by poor response to desmopressin (DDAVP) treatment (11). Desmopressin is a vasopressin analog to stimulate the release of endogenous VWF from endothelial cell stores. Desmopressin has been used for over 25 years to treat VWD and its mechanism of action has been reviewed extensively (12-14). Patients with Type 3 VWD have a severe bleeding tendency and in the majority of patients, an increase in VWF is not observed following treatment, or if it does occur, bleeding time is not shortened (15).

A VWD diagnosis is based on the patient's medical history and on laboratory test results. The diagnosis of the disease, especially in Type 1 VWD, may at times be problematic. Low levels of VWF:Ag and VWF:RCof can be difficult to interpret due to the fact that plasma levels of VWF in normal subjects exhibit a high degree of variability. Different factors can contribute to modifications in VWF levels: estrogens, thyroid hormones, diabetes, exercise, pregnancy, age, and ABO blood type. Individuals with blood type O show plasma levels of VWF that are 25% lower than those with other blood groups. In addition, patients with VWD can intermittently have VWF levels in a normal range (8). Therefore, all abnormal or normal results in individuals with high clinical suspicion should be confirmed.

1.1.2 Von Willebrand Disease Treatment

The aim of treatment in VWD is to correct 2 hemostatic defects: abnormal coagulation due to low levels of circulating FVIII and abnormal platelet adhesion, which translates into prolonged bleeding time. There are 3 treatment options for this disease: nonreplacement therapy, replacement therapy, and antifibrinolytic or topical agent administration (12,16,17). Patients may receive any 1 or all 3 treatment options at the same time.

In nonreplacement therapy for VWD, patients are treated with DDAVP. In replacement therapy for VWD, patients are treated with cryoprecipitate or plasma derived concentrates of VWF/FVIII to correct (at least partially) the hemostatic defect and control bleeding in patients. The effectiveness of the treatment of patients with severe VWD with VWF/FVIII concentrates has been demonstrated. Therefore, replacement therapy with FVIII concentrates that contain a large quantity of VWF is indicated in patients who do not respond to treatment with DDAVP or for whom DDAVP is contraindicated (18). Lastly antifibrinolytics or topical agents may also be used to treat VWD in some countries. These agents promote hemostasis and wound healing without substantially altering VWF plasma concentration (17).

Treatment is based on the type and severity of VWD, the severity of the hemostatic challenge, and the nature of the actual or potential bleeding (17). Patients with Type 1 VWD are mainly treated with DDAVP. However, the bleeding time in patients with a low amount of platelet VWF (Subtype 2B) may not be corrected, and a poor response to treatment with DDAVP is observed (8,9). The response of patients with Subtypes 2A, 2M, and 2N to DDAVP treatment is limited, as it promotes the release of an abnormal VWF; thus, bleeding time is generally not shortened. Desmopressin administration may be contraindicated in patients with Subtype 2B due to the possibility of platelet aggregation and thrombocytopenia (19). Patients who have Type 3 VWD rarely experience a clinically relevant increase in VWF:RCo or FVIII levels, and DDAVP is not considered effective treatment in these patients (17).

Fanhdi® is a highly purified, double inactivated anti-hemophilic factor (VWF/FVIII) concentrate prepared from human plasma manufactured by Instituto Grifols, S.A. Administered intravenously, Fanhdi has been commercially available in different countries since December 1994 for the prevention and control of bleeding in patients with hereditary or acquired hemophilia A (20). Since it is a concentrate of highly purified, lyophilized FVIII that contains VWF, the effectiveness of Fanhdi treatment in subjects with VWD was examined and shown to be an effective and safe replacement therapy in subjects with VWD to provide adequate hemostasis in surgical procedures and treatment of bleeding episodes (21,22). Fanhdi has been commercially available for VWD replacement therapy in several countries since June 2009 (21). The VWF concentrates of Fanhdi correct hemostatic abnormalities in subjects with VWD by re-establishing platelet adhesion to the vascular sub-endothelium at the site of vascular damage and by binding to endogenous FVIII to stabilize the protein and avoid rapid degradation (23).

1.2 Rationale

At the request of the Spanish Agency of Medicines and Medical Devices (AEMPS), Instituto Grifols, S.A is conducting a Phase 4, observational, multi-center, prospective, post-authorization cohort study examining the safety (including key safety parameters of inhibitor development [immunogenicity] and thrombogenicity) and clinical efficacy of long term use of Fanhdi in subjects with VWD according to the current guidelines (24). Data on the use of Fanhdi in routine clinical practice in the prophylaxis and/or treatment of subjects with VWD will be collected during an observation period of 12 months.

2 OBJECTIVES

The objective of this Phase 4, observational, multi-center, prospective, post-authorization cohort study is to examine the safety (immunogenicity and thrombogenicity) and overall clinical efficacy of long term use of Fanhdi in subjects with VWD.

2.1 Safety Objective

- To evaluate the safety (immunogenicity and thrombogenicity) associated with long term use of Fanhdi (see Sections 3.5.1.2 and 3.5.1.3)

2.2 Efficacy Objective

- To evaluate the overall clinical efficacy of Fanhdi in bleeding episodes (see [Section 3.5.2.1](#))

3 STUDY DESIGN

3.1 Study Design and Plan

This is a Phase 4, observational, multi-center, prospective, post-authorization cohort study examining the safety (immunogenicity and thrombogenicity) and overall clinical efficacy of long term use of Fanhdi in routine clinical practice in approximately 15 subjects with VWD. In this clinical study, subjects will be treated with Fanhdi according to the investigator's standard of care to achieve hemostasis. Enrolled subjects will be treated with Fanhdi as their sole source of VWF/FVIII concentrate for prophylaxis and treatment of all bleeding episodes and surgical or invasive procedures for an observational period of 12 months.

Data will be collected from the information generated during routine examinations and treatments as performed by the investigator per standard of care during an observation period of 12 months, starting with the first Fanhdi infusion. There will be no intervention with the prescribing habits or practices of the investigator's standard of care, however the investigator is expected to treat the subject within the approved labeling for dose and frequency of Fanhdi as described in [Section 3.1.1 \(23\)](#). Data collection for all subjects will include inhibitor development (immunogenicity), thrombogenicity, adverse events (AEs), bleeding episodes (spontaneous or traumatic bleeding), surgery or invasive procedure, duration and severity, assessment and achievement of hemostasis, and Fanhdi consumption. Data will be transcribed into electronic case report forms (eCRFs) by designated study center personnel.

3.1.1 Approved Fanhdi Dosing in the Treatment of Von Willebrand Disease

To achieve hemostasis in subjects with VWD, 40 to 80 IU/kg VWF (VWF:RC₀) and 20 to 40 IU/kg FVIII:C are recommended. An initial dose of 80 IU/kg VWF may be required, especially in subjects with Type 3 VWD where maintenance of adequate levels may require greater doses than in other VWD types. An appropriate dose should be re-administered every 12 to 24 hours. Treatment dose and duration is dependent on the clinical status of the subject, the bleeding type and severity, and VWF:RC₀ and FVIII:C levels.

Continued treatment with Fanhdi may cause an excessive rise in FVIII:C. After 24 to 48 hours of treatment, the investigator should reduce treatment dose and/or duration.

3.2 Selection of Study Population

3.2.1 Inclusion Criteria

A subject who will be treated with Fanhdi must meet all the following inclusion criteria to be eligible for participation in this study:

1. Male or female subjects ≥ 18 years of age diagnosed with hereditary VWD of any type and severity who require replacement therapy with VWF/FVIII concentrates when desmopressin (DDAVP) treatment alone is ineffective or contra-indicated.
2. Subjects with a history of receiving prior treatment with VWF concentrates due to bleeding episodes and/or surgery or invasive procedures (on demand or prophylaxis).
3. Subjects who are expected to experience bleeding episodes and/or surgeries or invasive procedures (including elective surgeries) requiring replacement therapy in the future or with active bleeding at the time of inclusion.
4. Subjects who are willing and able to provide written informed consent or have an authorized representative able to provide written informed consent on behalf of the subject in accordance with local law and institutional policy.

3.2.2 Exclusion Criteria

Subjects with data meeting any of the following exclusion criteria are NOT eligible for participation in this study:

1. Subjects diagnosed with acquired VWD.
2. Subjects with a congenital or acquired platelet function disorder or other concomitant processes that may interfere with coagulation.
3. Subjects who are positive for anti-VWF or anti-FVIII antibodies (≥ 0.5 Bethesda units [BU]) or has been positive in the history of their disease.
4. Subjects with a known intolerance to any substance contained in Fanhdi.
5. Subjects with a history of anaphylactic reactions to blood or blood components.
6. Subjects who are participating in another clinical study involving an investigational treatment or have participated in one in the past 4 weeks.
7. Subjects who, in the opinion of the investigator, may have compliance problems with the protocol.

3.2.3 Subject Withdrawal Criteria

Subjects may withdraw or be withdrawn from the study for the following reasons:

1. A severe or serious adverse event (SAE), which, based on medical judgment, prevents completion of participate on in the study (see [Section 4.3](#) for classification of adverse events).
2. Development of VWF/FVIII inhibitors*
 - At a titer ≥ 0.5 BU or
 - At a titer < 0.5 BU that renders Fanhdi treatment ineffective in providing hemostasis.
3. Treatment with other VWF/FVIII concentrates while in the study.
4. Treatment with immunosuppressive drugs.
5. At their own request or at the request of their legally acceptable representative.

6. If, in the investigator's opinion, continuation in the study would be detrimental to the subject's well-being.
7. Determination of ineligibility based on eligibility criteria.
8. Termination of the study by a regulatory authority (see [Section 5.5](#)).

* If the expected VWF/FVIII plasma activity levels are not attained or if bleeding is not controlled with an appropriate dose, it is recommended that an assay should be performed to determine the development of VWF/FVIII inhibitors as per standard of care. In subjects with high levels of inhibitors, Fanhdi therapy may not be effective and other therapeutic options should be considered ([23](#)).

The reason for withdrawal should be recorded in the eCRF and subject's source documents. If a subject withdraws after treatment due to an AE, the study center will attempt to obtain all possible follow-up safety data from that subject.

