3.4 Methods and Timing for Recording Study Parameters

In this clinical study, subjects will receive the most suitable dose of Fanhdi, according to the investigator's discretion, to achieve satisfactory hemostasis. There will be no intervention with the prescribing habits or practices of the investigator's standard medical care; however, the investigator is expected to treat the subject within the approved labeling for dose and frequency of Fanhdi (see [Section 3.1.1](#)).

Subjects will be followed for 12 months after the first infusion of Fanhdi, in which information gathered from any episode (spontaneous or traumatic bleeding), surgery or invasive procedure, and the response to treatment and consumption of Fanhdi will be collected.

An assessment of the overall clinical efficacy of Fanhdi throughout the study will be performed and collected by the investigator utilizing a 4-point rating scale (evaluated as "excellent," "good," "poor," or "no response" in response to therapy with Fanhdi received by the subject in a hospital or another location under the investigator's direct supervision). Clinical efficacy assessment ratings are described in Table 3-1 ([25](#)).

Table 3-1 Assessment of Clinical Efficacy

Rating	Clinical Efficacy	
Excellent	Hemostasis comparable with that expected for individuals without known bleeding disorders	No increase in FVIII/VWF dosing required
Good	Hemostasis slightly inferior to that expected for individuals without known bleeding disorders	Minor increase in FVIII/VWF dosing required
Poor	Reduced hemostasis is compared with that expected for individuals without known bleeding disorders	Significant increase in FVIII/VWF dosing required; no need for alternative therapy
No Response	Severe bleeding despite FVIII/VWF therapy	Significant increase in FVIII/VWF dosing required and/or need for alternative therapy to control bleeding

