To determine the clinical efficacy of Fanhdi for bleeding episodes in subjects with VWD, information will be collected on the nature, location, duration (time to hemostasis of the bleed between the start of the first Fanhdi infusion and the cessation of bleeding) and severity of the bleeding episodes as assessed by the investigator.

In addition, the number of infusions and the total amount of Fanhdi dosed for bleeding episodes and the use of additional blood derivatives (ie, FVIII concentrates, transfusions [plasma, platelets, and RBCs], cryoprecipitate) or antifibrinolytic agents will be collected. Efficacy data will be recorded in the appropriate eCRF and in the subject's source documents.

Information on the clinical correction of hemostasis and overall clinical efficacy of bleeding episodes as assessed by the investigator utilizing a 4-point rating scale ("excellent," "good," "poor," or "no response" [Table 3-1, 25]) will be collected over the course of 12 months of therapy.

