5.3 Safety Analysis

The safety analyses will be addressed by listing and tabulation of AEs (includes suspected ADRs), clinical laboratory tests including inhibitor (immunogenicity) and functional activity testing, thrombogenicity, vital signs, and physical examinations. Data will be described using descriptive analyses.

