5.4 Efficacy Analysis

For bleeding episodes, the bleeding duration, severity, achievement of adequate hemostasis, and overall clinical efficacy will be summarized. Also, the number of Fanhdi infusions and the total amount of Fanhdi dosed will be summarized. The proportion of bleeding episodes in which good or excellent clinical efficacy were achieved will also be summarized.

For surgeries or invasive procedures, the surgery type, severity of bleeding episodes, achievement of adequate hemostasis, and overall clinical efficacy will be summarized. Also, the number of Fanhdi infusions and the total amount of Fanhdi dosed will be summarized. The proportion of surgeries or invasive procedures in which good or excellent clinical efficacy were achieved will also be summarized.

For long-term observation, the long-term overall clinical efficacy will be summarized. Also, the number of bleeding episodes and surgeries or invasive procedures will be summarized. The number of infusions, exposure days, and dose per month will be summarized, in addition to the mean quantity of Fanhdi per bleeding episode and/or surgery or invasive procedure.

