5.5 Study Size Determination

Approximately 15 subjects are planned to be enrolled in this clinical study. The sample size is based on clinical considerations and was not formally calculated.

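### Section 3.2.3 lets observation, not just Fanhdi, end because of an inhibitor or a switch of concentrate, so the 12-month measures can be truncated by failure

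*Protocol*

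**What the plan says.** Section 3.2.3 lists reasons for which a subject may leave, or be taken out of, the study. Reason 2 is a VWF/FVIII inhibitor, either at 0.5 BU or more, or "At a titer < 0.5 BU that renders Fanhdi treatment ineffective in providing hemostasis". Reason 3 is "Treatment with other VWF/FVIII concentrates while in the study". After a withdrawal due to an adverse event the centre tries to obtain further safety data. Nothing is stated for other withdrawals, and nothing for efficacy data.

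Elsewhere the same events are outcomes:

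- Section 2.1 makes immunogenicity in long-term use part of the safety objective.
- Table 3-1 (Section 3.4) includes "need for alternative therapy to control bleeding" in the definition of No Response.
- Section 3.5.2.1 collects "the use of additional blood derivatives (ie, FVIII concentrates, transfusions [plasma, platelets, and RBCs], cryoprecipitate" as efficacy information for bleeds. Section 3.5.2.2 does the same for procedures, and Section 3.3.2 lists use of other hemoderivatives per bleed as an efficacy variable.

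On follow-up, Section 3.4 says "Subjects will be followed for 12 months after the first infusion of Fanhdi". On analysis, Section 5.4 says "For long-term observation, the long-term overall clinical efficacy will be summarized". Section 3.5.2.3 leaves that rating to the investigator and gives neither a time point nor a provision for subjects who leave early.

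**The concern.** When the event that ends observation is itself a sign of failure, the missing data depend on the outcome. The protocol asks for 12 months of follow-up, yet allows follow-up to stop when an inhibitor appears or another concentrate is used. The exposed measures are those that need the whole year: the long-term rating, the number of bleeds, and consumption per subject and year.

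Withdrawal is optional, so who leaves after a failure may differ between investigators, who also assign the ratings. Section 5.6 does not mention this among the study's limitations. With about 15 subjects, one unrated failure moves a subject-level percentage by roughly 7 points. Data come from routine medical records (Section 3.5.4.1), so nothing in the design requires collection to stop when the product is stopped.

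**Working it through.** **Inputs.** About 15 subjects; Section 5.5 says "The sample size is based on clinical considerations and was not formally calculated". Follow-up is 12 months (Section 3.4). Section 5.3 says of safety "Data will be described using descriptive analyses", and Section 5.4 provides only summaries. The protocol states no failure rate, bleeding rate or dropout rate, so there is no figure to reproduce. The failure counts and bleeding rates below are assumptions.

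**Step 1: what is kept and what is lost.**

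| | Exit for an inhibitor | Exit for another concentrate, no adverse event |
|---|---|---|
| In the analysis set | Yes (5.1) | Yes (5.1) |
| Triggering event reported | Yes: titer listed (5.3.2) | Yes: any triggering bleed is rated (3.5.2.1) |
| Safety follow-up after exit | Yes: a laboratory abnormality causing withdrawal is an adverse event (4.8), followed under 3.2.3 and 4.2, and under 4.10 where serious or a suspected reaction | None stated |
| New adverse events after exit | Recording ends on the last day of participation (4.2, 4.8) | Same |
| Efficacy data after exit | None stated | None stated |
| Long-term rating required at exit | No (3.5.2.3, 5.4) | No (3.5.2.3, 5.4) |

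**Step 2: long-term rating.** Let *w* subjects leave for these reasons after failing, with all others rated good or excellent. Counting everyone gives (15 − w)/15. If the leavers have no rating, the result is (15 − w)/(15 − w) = 100%. The overstatement is w/15. Intervals are exact (Clopper-Pearson) 95%.

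| w | All 15 counted | Leavers unrated | Difference |
|---|---|---|---|
| 1 | 14/15 = 93.3% (68.1 to 99.8) | 14/14 = 100% (lower limit 76.8) | 6.7 points |
| 2 | 13/15 = 86.7% (59.5 to 98.3) | 13/13 = 100% (lower limit 75.3) | 13.3 points |
| 3 | 12/15 = 80.0% (51.9 to 95.7) | 12/12 = 100% (lower limit 73.5) | 20.0 points |

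**Step 3: proportion of bleeds rated good or excellent.** Assume *b* bleeds per subject-year. Each failing subject has b/2 good bleeds, then one failed triggering bleed, and every later bleed would also fail. Full follow-up gives [(15 − w)b + wb/2]/(15b) = 1 − w/30, that is 96.7%, 93.3% and 90.0% for w = 1, 2, 3. Stopping after the triggering bleed changes the denominator to (15 − w)b + w(b/2 + 1):

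| b | w = 1 | w = 2 | w = 3 |
|---|---|---|---|
| 2 | 29/30 = 96.7% | 28/30 = 93.3% | 27/30 = 90.0% |
| 4 | 58/59 = 98.3% | 56/58 = 96.6% | 54/57 = 94.7% |
| 8 | 116/117 = 99.1% | 112/114 = 98.2% | 108/111 = 97.3% |
| 12 | 174/175 = 99.4% | 168/170 = 98.8% | 162/165 = 98.2% |

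The upward shift is nil at 2 bleeds a year and 1.6 to 8.2 points at 4 to 12. It never reaches 100%, because the triggering bleed stays in. It also presumes that the later bleeds would have been treated with Fanhdi. After a switch they would not be Fanhdi episodes, and this shift would not arise.

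**Step 4: counts.** Under the same assumptions with b = 8, a failing subject contributes 8/2 + 1 = 5 bleeds instead of 8. Uncorrected 12-month bleed counts would be too low.

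**The case against.** The strongest defence is that the failures are not hidden. Section 5.1 puts every enrolled subject in all analyses, inhibitor titers are listed, the reason for withdrawal is recorded, and the triggering bleed is rated. The efficacy objective (Section 2.2) concerns bleeding episodes, where that bleed counts. All of this stands. A reader might infer that failures drop out before the summaries, but the protocol does not say so.

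Three other stronger readings also fail:

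- *Loss of effect is a general reason to leave.* It is listed only together with an inhibitor below 0.5 BU.
- *The course of an inhibitor is cut off when it appears.* Section 4.8 makes an inhibitor that causes withdrawal an adverse event, and it is then followed.
- *Every such subject should be rated No Response.* Table 3-1 ties that rating to severe bleeding despite therapy. An inhibitor with preserved hemostasis, or a switch for reasons other than efficacy, does not meet it.

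It is also fair that withdrawal is permitted rather than required, that nothing bars a rating at exit, and that Section 5 leaves data handling to the SAP. Current or past inhibitor positives are excluded at entry, so 1 to 3 failures may be too many. Finally, Section 3.1 makes Fanhdi the sole concentrate, which explains reason 3, and *FVIII concentrates* in Section 3.5.2.1 is not identical to *other VWF/FVIII concentrates* in Section 3.2.3. The two passages overlap rather than flatly contradict each other.

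What the defence does not answer is the collection rule. An analysis set cannot supply ratings that were never taken, and an SAP cannot recover data that the protocol stopped collecting.

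**Conclusion.** The concern holds in a limited form. Section 3.2.3 allows follow-up to be truncated by the study's own outcomes. What is lost is efficacy data after any such exit, safety data after an exit without an adverse event, and an assured long-term rating. The long-term rating can be biased upward and uncorrected bleed counts downward, both in the product's favour. Consumption per subject and year rests on an incomplete year.

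The overstatement of the long-term rating is 6.7, 13.3 or 20.0 points for 1, 2 or 3 unrated failures among 15. That rests on three assumptions: the number of failures, no rating at exit, and success in everyone else. With a rating at exit it disappears. The study is descriptive, so no test or decision threshold is affected. This should be fixed; it is not a fatal flaw.

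**What to change.** 1. **Section 3.2.3.** Separate stopping Fanhdi from leaving the study. Record an inhibitor or the use of another concentrate as an event, and continue record-based data collection to month 12 unless consent is withdrawn. Whether Fanhdi is stopped, and what follows clinically, stays with the investigator.
2. **Sections 3.5.2.3 and 5.4.** Require the investigator's long-term Table 3-1 rating of Fanhdi at the time it is stopped, and keep these subjects in the denominator. Lack of effect, or need for alternative therapy to control bleeding, counts as not good or excellent. Count and report separately inhibitors with preserved hemostasis and switches unrelated to efficacy.
3. **Reconcile** Section 3.2.3, where another concentrate is a reason to leave, with Sections 3.3.2, 3.4 (Table 3-1), 3.5.2.1 and 3.5.2.2, where such use is collected and rated as an outcome.

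The cost is amendment wording, some extra record abstraction and possibly a less favourable efficacy figure. No extra visits are needed.
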